Study Design. The study is a randomized, open-label, comparative effectiveness clinical trial in 180 patients (60 children, 120 adults) with GERD or any stomach acid mediated condition that will require a PPI. Patients will volunteer to be randomized to either conventional PPI treatment or genotype-supported PPI treatment. All participants will have symptoms of GERD or related diseases who are candidates for PPI therapy or who are on PPI therapy and classified as refractory GERD. Adult patients will be enrolled at UF Health Gastroenterology Clinics and children will be enrolled at the Nemours Children's Hospital Gastroenterology Clinics. After obtaining informed consent, participants will be genotyped and randomly assigned to either conventional treatment or genotype-supported PPI therapy using a randomization table. At NCH, study participants in the control/conventional arm will be blinded on CYP2C19 metabolizer status. Study staff members will not be blinded to any study procedures or determinations as this will improve and facilitate study feasibility. At the end of study period (i.e. 8-12 weeks) study participants in the control/conventional arm will be revealed of metabolizer phenotype status. We will also collect data from the health records for up to 24 months after enrollment on upper respiratory infection (cold), sore throat, strep throat, bronchitis, pneumonia, ear infection, acute sinusitis (sinus infection), bone fractures, renal function, and gastrointestinal infections for preliminary assessment of the effects of CYP2C19-supported PPI dosing on adverse effects.

Participation stipends. Each participant will receive \$25 dollars at the end of study participation. Participants must have completed all study procedures by the end of the study period in order to receive the complete study stipend. If a study participant decides to withdraw from study before the end of study period (before 3 months), the participant will receive a pro-rated stipend. A deposit will be provided in a single CT Payer master card. Each participant will be provided a CT Payer (master card) at the moment of consent. The CT Payer card will be uploaded with the stipend at the end of study participation. Participants whom insurance coverage is limited, a separate deposit will be provided to cover study therapy expenses. We expect to incur in study drug expenses for participants with higher PPI dose prescriptions than conventional dosing (i.e. RMs and UMs).

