Genetic results and clinical decision support. Results will be entered in the participant's electronic health record; genotype results for participants in the control/conventional arm will not be made available to patients/families through the secure patient portal in the EMR to maintain blind status. PPI recommended dosing will be made available to GI providers in the EMR for genotype-guided dosing. PPI templates will include phenotype, genotype, dosing recommendations, and educational information. Participants in the conventional arm will be prescribed the conventional PPI dose.

To minimize risks associated with genetic studies, all results of genetic tests and patient data will be stored in a secure database which is accessible only to study investigators. Genotype and phenotype data will be stripped of all identifiers prior to submission to the NIH dbGAP repository.

Assessment of PPI adverse events and efficacy. Our primary outcome will be a directed interview and questionnaire by study personnel at baseline and every following week up to 12 weeks of participation for efficacy of PPI therapy and for adverse outcomes for the study period: upper respiratory infection (cold), sore throat, strep throat, bronchitis, pneumonia, ear infection, acute sinusitis (sinus infection), and gastroenteritis. We have experience using the questionnaire to evaluate the safety of PPI treatment in children. The prevalence of each respiratory and gastrointestinal symptom will be compared in participants receiving conventional vs. genotype-supported dosing. As secondary outcomes, the efficacy and safety (adverse event score) of PPI therapy will be determined from scores from patient and parent-proxy reported outcomes: the GASP-Q, the validated SN-5 Pediatric Sinonasal Symptom Survey and validated PedsQL™ Gastrointestinal Symptoms Module. Efficacy and adverse events questionnaires will be completed via an electronic questionnaire on a weekly basis and stored in REDCap.

At Nemours Children's Hospital continuous monitoring on study metrics will be offered by study staff. Study metrics will include Gasp-Q, PedsQL™ Gastrointestinal Symptoms Module, SN-5 Pediatric Sinonasal Symptom Survey and Safety Q.

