Statistical analysis. We will have two primary hypotheses tested in this pragmatic clinical trial: 1. Hypothesis: RMs (1 or 2 GOF alleles) in the genotype-supported arm have better GERD control than RMs in the usual care group 2. Hypothesis: PMs (1 or 2 LOF alleles) in the genotype-supported group have fewer adverse effects (composite of URI/GI infections, kidney adverse effects, bone fracture) than PMs in the usual care group. Continuous variables will be compared between the genotype-supported group and the usual care group using t-test, and categorical variables will be compared using the chi-squared test. The hypotheses will be tested by logistic regression analysis to estimate the odds ratios and 95% confidence intervals for GERD control rate in the RM patients between the two arms and for the adverse events between the PM patients between the two arms. Time to-event analysis will be performed using Kaplan Meier method and a Cox regression model. Significant covariates associated with the events will be adjusted for in the multivariable models. All analysis will be performed in SAS 9.4 (Cary, NC).

We will also have a composite analysis that is conducted in the same manner that combines efficacy and safety and tests the hypothesis that genotype supported PPI dosing leads to better PPI efficacy and safety, as determined by composite of refractory GERD, and adverse effects.

Finally, we will evaluate the influence of genotype-supported dosing recommendations and will evaluate the percentage of the time when a dosing recommendation was made and accepted by the treating clinician, to provide practical data on the willingness of clinicians to adopt this approach. We will also collect patient- and provider-level survey data on attitudes about pharmacogenetics testing; using survey tools adapted from those utilized by other IGNITE groups. These will be shared for network-wide analyses, but because of the number of patients we will study, we should also have sufficient data to perform analyses on our patients along.

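### At Nemours only control families are blinded to metabolizer status, so the family-reported infections in hypothesis 2 come from differently informed reporters and need a prespecified record-based check

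*Combined protocol and SAP*

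**What the plan says.** All of this comes from the Nemours part of the combined document, under the study design heading for Aim 2.

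- **Who is blinded.** Study Design: "At NCH, study participants in the control/conventional arm will be blinded on CYP2C19 metabolizer status". At the end of the study period, "study participants in the control/conventional arm will be revealed of metabolizer phenotype status".
- **How the blind is kept.** Genetic results and clinical decision support: "genotype results for participants in the control/conventional arm will not be made available to patients/families through the secure patient portal in the EMR to maintain" the blind. No sentence withholds results from genotype-arm families.
- **Staff.** Study Design declares the trial open-label and adds: "Study staff members will not be blinded to any study procedures or determinations".
- **Who reports.** Inclusion Criteria requires the parents and/or child to have internet and email access for the weekly forms. Assessment of PPI adverse events and efficacy says: "Efficacy and adverse events questionnaires will be completed via an electronic questionnaire on a weekly basis". The same paragraph describes a directed interview by study personnel. The listed conditions are colds, sore throat, strep throat, bronchitis, pneumonia, ear infection, sinusitis and gastroenteritis.
- **What is compared.** "The prevalence of each respiratory and gastrointestinal symptom will be compared in participants receiving conventional vs. genotype-supported dosing". Statistical analysis makes it a primary hypothesis that "PMs (1 or 2 LOF alleles) in the genotype-supported group have fewer adverse effects". That composite also includes kidney events and fractures.
- **Second source.** Study Design collects the same kinds of infection from health records for up to 24 months, for preliminary assessment. Statistical analysis does not use the records to check hypothesis 2.

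**The concern.** The sponsor judged a family's knowledge of metabolizer status worth masking, and then masked one arm. In the genotype-supported arm, the family of a poor or intermediate metabolizer may know that the child clears the drug slowly and that a lower dose was recommended for that reason. A control family with the same genotype is kept from knowing it. Both then report, week by week, whether the child had a cold or a sore throat.

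Many of these complaints are mild, and whether they are recorded depends partly on the reporter's expectations. Reassured families may report less, which would favour the hypothesis; alerted families may report more. A reporting difference of either kind looks the same as an effect of the lower dose. No blinded assessor or adjudication of infections is described, and a larger sample would not remove the bias. At stake is any claim that genotype-supported dosing reduces infections.

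**Working it through.** **1. Inputs**

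- Nemours children: 60 (Study Design), about 30 per arm.
- Share with one or two loss-of-function alleles, which Statistical analysis groups as PM: 20% + 1.7% = 21.7% (Table 1), or 178/600 = 29.7% (Power calculation).
- Planned effect: 29% relative reduction, 80% power, 89 per arm, alpha 0.05 (Power calculation). Sidedness and usual-care risk are not given; two-sided is assumed.
- Reporting difference: no figure in the documents. Assumed: 10%, 15% or 20% fewer affected children reported in the genotype arm.

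**2. Usual-care risk implied by the plan's 80% power**

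The 80% cannot be reproduced directly without a usual-care risk, so I solved for the risk that yields it. With d = p1 − p2, p̄ the mean of p1 and p2, SE0 = √(2p̄(1−p̄)/n) and SE1 = √((p1(1−p1) + p2(1−p2))/n):

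power = Φ((d − 1.96·SE0)/SE1)

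For p1 = 0.704, p2 = 0.71 × 0.704 = 0.500 and n = 89: d = 0.204, SE0 = 0.0734, SE1 = 0.0718. Then (0.204 − 0.144)/0.0718 ≈ 0.84, and Φ(0.84) ≈ 0.80. The implied usual-care risk is about 0.70.

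**3. Number of children exposed to the mechanism**

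- Table 1 share: 0.217 × 60 = 13.0, about 6.5 per arm.
- Power-statement share: 0.297 × 60 = 17.8, about 8.9 per arm.

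This gives roughly 7 to 9 per arm.

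**4. Chance of a false result of fewer events**

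Set the true risk to 0.704 in both arms and the reported genotype-arm risk to 0.704 × (1 − r), and apply the same formula. Two worked cases:

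- n = 7, r = 0.20: d = 0.141, SE0 = 0.2575, SE1 = 0.2548; (0.141 − 0.505)/0.2548 = −1.43, which gives 7.7%.
- n = 9, r = 0.10: d = 0.070, SE0 = 0.2219, SE1 = 0.2212; (0.070 − 0.435)/0.2212 = −1.65, which gives 5.0%.

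| Per arm | r = 0 | r = 0.10 | r = 0.15 | r = 0.20 |
|---|---|---|---|---|
| 7 | 2.5% | 4.6% | 6.0% | 7.7% |
| 9 | 2.5% | 5.0% | 6.7% | 8.8% |

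The normal approximation is rough at these sizes. With an assumed usual-care risk of 0.50 and 9 per arm, the three values fall to 4.0%, 5.0% and 6.2%.

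**5. Shift in the estimate**

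0.10/0.29 = 0.34 and 0.20/0.29 = 0.69, so one third to two thirds of the target. This shift does not depend on sample size. Over-reporting by the same proportions would move the estimate equally far the other way.

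**The case against.** **The trial is open-label by design.** Nothing hides arm assignment from families, the interviewers are unblinded, and the Nemours dosing table links dose to phenotype, so a family could infer status from a changed dose. Disclosure may also be part of the pragmatic strategy under test. This stands. It means that equalising disclosure would remove only part of the bias, but it does not make the two groups of reporters equally informed.

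**Release to genotype-arm families is inferred.** This also stands. A reader might take the documents to say that these families are shown their result. They say only that control families are not, and are told at the end. Consent pages, where disclosure could be stated, were not available for review.

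**The size is easily overstated.** A reader might apply the power statement's 89 per arm and conclude that the false-benefit chance reaches 17%, 31% or 50% for r = 0.10, 0.15 or 0.20. The documents do not support that. Those 89 belong to a 600-participant trial, while Study Design now plans 180 patients, of whom 60 are children. The weekly family forms and the portal rule are Nemours procedures. In the UF protocol, adult adverse outcomes come from medical-record review.

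**The assumed reporting loss is strong.** A child counts as unaffected only if every episode goes unreported. If families omitted 10 to 20% of episodes, and episodes were Poisson at a risk of 0.704 (mean −ln 0.296 = 1.217), affected children would fall to 1 − exp(−1.217 × 0.9) = 0.666 or 1 − exp(−1.217 × 0.8) = 0.622. That is about 5 to 12% fewer, so the 10 to 20% range is towards the high side.

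**Hypothesis 2 is wider than the weekly form.** Kidney events and fractures are not on the form's list. The concern covers the infection part only, and the shift in the full composite would be diluted.

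**Conclusion.** The concern holds for the infection part of hypothesis 2 at Nemours. The blind is written for one arm, families are the weekly reporters, and no analysis tests whether an infection difference survives without their reports. At the planned size, the false-benefit chance rises from 2.5% to roughly 5 to 9%, and the estimate shifts by one third to two thirds of the 29% target. These figures rest on an implied usual-care risk of about 0.70, an assumed 10 to 20% loss of affected children in the genotype arm, no true effect, and a comparison confined to Nemours children. Pooling with adults whose infections come from records would dilute the shift.

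A reader might infer that the bias must favour genotype-supported dosing. The documents give no basis for a direction; the calculation follows the favourable direction only because that is where a false claim of benefit would arise. The point limits what may be concluded from family reports and does not show that the trial's result would be wrong.

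**What to change.** **In Statistical analysis (Nemours protocol):** prespecify a sensitivity analysis of hypothesis 2 that counts only infections documented in the health record during the 12-week questionnaire period, with kidney events and fractures counted as in the main analysis. State in advance that an infection benefit seen only in family-reported data, and not in the same direction in the records, will be described as unconfirmed.

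**Cost:** one extra analysis of data that Study Design already collects. It will be imprecise with so few children, and records miss mild episodes for which no care was sought. Agreement in direction is therefore the realistic test, not significance.

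**Optional:** the sponsor may consider the same portal-release timing for families in both arms, with the treating clinician still receiving the genotype and recommendation in the genotype-supported arm. Genotype-arm families would wait up to 12 weeks for the portal result, and masking would be only partial. If this is not adopted, one sentence saying when genotype-arm families receive the result would remove the present ambiguity.

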While other adverse effects such as suggestions of risk of myocardial infarction, and dementia have been associated with PPIs, we will not focus on these outcomes as the power in our study will not be sufficient to detect these outcomes. Additionally, for dementia the risk has been observed in PPI users over the age of 75, and we are likely to have limited numbers of patients in our analysis of this age group.

**Case for CYP2C19 genotype-guided PPI dosing.** The data above provide substantial evidence for the link between CYP2C19 genotype, PPI pharmacokinetics, efficacy and adverse effects. Use of PPIs has increased dramatically in the last decade, driven in part by an impression that they are “benign drugs”. As a result they are often prescribed as long term therapy in multiple different patient populations. It is not uncommon for patients to be on PPI therapy for multiple years or even “indefinitely”, despite no clear indication being present.

As described in this application, long-term PPI use has been associated with potentially serious adverse events. Recent high profile publications have increased awareness among clinicians of potential risks of PPIs, and the need for more rational use and dosing. In many cases data suggest the risk of adverse effects are dose related, which implies that safety of these drugs can be improved through rational dosing based on CYP2C19 genotype. Although the case for pharmacogenetic testing of CYP2C19 to guide PPI therapy has been made recently, additional evidence is needed. This project is significant because it will add to the evidence of associations between CYP2C19 genotype and adverse outcomes to PPI therapy and will also prospectively test the hypothesis that genotype-guided PPI dosing is safer than conventional dosing in children and adults. It will also provide practical experience on the clinical implementation of CYP2C19 genotype-guided PPI dosing.

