#### **STUDY DESIGN\_ Focus on Aim2 for Nemours Children's Hospital**

**Aim 2: Implement pharmacogenetic testing of the CYP2C19 gene-PPI drug pair in adults at UF Health and in children at Nemours Children's Hospital in the context of a comparative effectiveness genotype-supported vs. conventional PPI dosing trial.**

Overview. We have designed a comparative effectiveness clinical trial testing conventional PPI dosing with genotype-supported dosing with clinically meaningful outcomes to determine the feasibility of genetic testing in a pediatric and adult setting. The primary outcome is a composite end point of upper respiratory infections pneumonia, acute gastroenteritis, adverse kidney effects and bone fractures.

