Power calculation. Briefly, with 600 participants in the trial, we will have 80% power at alpha level of 0.05 to detect a relative risk of 1.35 or higher in the GERD control within RM patients in the usual care vs. the genotype-supported arm. This assumes that among the 600 participants, 33% will have the RM phenotype, and half will be randomized to each arm of the study. For the adverse event hypothesis, with 600 patients, we expect to have 178 PM patients, with 89 patients in each arm. At alpha level of 0.05, we will have 80% power to detect relative risk reduction of 29% or more in the adverse events for PM patients in the genotype supported group compared to those in the usual care group.

Clinical Trials.gov. This trial requires registration in ClinicalTrials.gov.

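### The Nemours plan puts eight separate infection comparisons under its primary outcome and never says that they rank below the composite safety endpoint or are exploratory

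*Combined protocol and SAP*

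**What the plan says.** All of this is in the Nemours part of the combined document.

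- **Assessment of PPI adverse events and efficacy.** The section opens with "Our primary outcome will be a directed interview and questionnaire by study personnel at baseline and every following week up to 12 weeks". The adverse outcomes it lists are "upper respiratory infection (cold), sore throat, strep throat, bronchitis, pneumonia, ear infection, acute sinusitis (sinus infection), and gastroenteritis", which makes eight conditions. It then states "The prevalence of each respiratory and gastrointestinal symptom will be compared in participants receiving conventional vs. genotype-supported dosing", and only after that sentence turns to secondary outcomes.
- **Overview of Aim 2.** "The primary outcome is a composite end point of upper respiratory infections pneumonia, acute gastroenteritis, adverse kidney effects and bone fractures".
- **Statistical analysis.** "We will have two primary hypotheses tested in this pragmatic clinical trial". The first is GERD control in rapid metabolizers. The second is an adverse-effect composite in poor metabolizers (carriers of one or two loss-of-function alleles). A general sentence adds that "categorical variables will be compared using the chi-squared test".
- **Power calculation.** The level appears only for those two hypotheses; for the adverse-event one it reads "At alpha level of 0.05, we will have 80% power to detect relative risk reduction of 29% or more".
- **Study Design.** The 24-month health-record data are described as a preliminary assessment. That wording does not extend to the weekly 12-week questionnaire.

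**The concern.** Read in order, the eight whole-arm comparisons belong to the primary outcome, because the secondary outcomes start only in the next sentence. Two other sections place the primary safety question elsewhere, in a composite, and one of them restricts it to poor metabolizers. No sentence connects the two descriptions, so an analyst or author could present any one of the eight infections as a primary-outcome result.

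The background, under the case for genotype-guided dosing, says the project will "prospectively test the hypothesis that genotype-guided PPI dosing is safer than conventional dosing in children and adults". If dosing made no difference, an isolated p-value below 0.05 for one infection could still be reported as support for that statement, or equally as evidence of harm, in a trial that informs dosing in children.

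**Working it through.** **The plan's own figure.** The documents give no error rate for the eight comparisons. The nearest stated figure is 80% power for a 29% relative risk reduction with 89 poor metabolizers per arm at 0.05. The control event rate is not given. A two-sided two-proportion calculation gives 49.8% power at an assumed control rate of 50%, 64.4% at 60% and 79.4% at 70%. The figure is attainable but cannot be verified. It concerns the composite in poor metabolizers, not the eight infections.

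**Inputs from the documents**
- Number of comparisons: k = 8 (seven respiratory conditions and gastroenteritis).
- Test: chi-squared (Statistical analysis).
- Sample: 60 children (Study Design).

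**Assumptions**
- 30 children per arm, which takes 1:1 allocation at Nemours.
- Two-sided 0.05 for each item, inferred from the Power calculation.
- The 12-week risks and the correlation between infections, which the documents do not give.

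The UF adults do not enter. Their protocol collects symptom scores at baseline and 12 weeks and takes infections from record review.

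**Step 1: independent tests.** P(at least one p < 0.05) = 1 - (1 - 0.05)^8 = 1 - 0.6634 = 0.337.

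**Step 2: correlated test statistics.** With eight equally correlated normal statistics the probability is 0.299 at correlation 0.3, 0.251 at 0.5 and 0.191 at 0.7.

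**Step 3: the planned test at the planned size.** Null trials were simulated with 30 children per arm, identical risks in both arms, binary outcomes from a correlated latent normal, and the uncorrected chi-squared test. There were 8,000 trials per cell in the first four rows and 20,000 in the last two.

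| Assumed 12-week risks (%) | Latent corr. 0 | 0.3 | 0.5 | 0.7 |
|---|---|---|---|---|
| all eight at 50 | 0.342 | 0.332 | 0.309 | 0.265 |
| 50, 40, six at 30 | 0.326 | 0.319 | 0.290 | 0.250 |
| 40, 30, 15, 15, 10, 10, 10, 2 | 0.320 | 0.313 | 0.292 | 0.267 |
| 30, 20, 10, 5, 5, 5, 5, 2 | 0.248 | 0.235 | 0.233 | 0.212 |
| 30, 20, 10, 5, 4, 3, 2, 2 | 0.198 | 0.195 | 0.188 | 0.174 |
| 15, 10, 5, 3, 2, 2, 1, 1 | 0.148 | 0.144 | 0.141 | 0.130 |

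Repeating the first four rows with 20,000 trials moved no entry by more than 0.01. The range is about 0.13 to 0.34, or 2.6 to 6.8 times 0.05 (0.13/0.05 and 0.34/0.05). Because the arms are exchangeable under no effect, such results favour either arm about equally often.

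**Step 4: sensitivity to the test.** Fisher's exact test gives about 0.06-0.20 in the first four rows and about 0.03-0.06 in the last two. The UF plan names that test; the Nemours statistical text names only chi-squared.

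**The case against.** The strongest reply is that the plan does declare its primary hypotheses. There are two, and the safety one is a composite in poor metabolizers. The single infections are not among them, they are not powered, no significance level is attached to them, and the chi-squared test comes from a general sentence. The same assessment section also makes an adverse-event score a secondary outcome. On this view the eight comparisons are simply summaries, and the *safer* sentence is background.

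Much of this stands, and it rules out some stronger readings that a reader might infer:

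- *The plan runs eight confirmatory tests at 0.05.* It does not say so. The level is an inference from the Power calculation.
- *There is no hierarchy at all.* A composite is named as primary in two places. What is missing is a statement that the single-infection comparisons rank below it.
- *The trial's primary false-positive rate is about one in three.* The 13-34% is the chance of at least one nominally significant infection. It does not apply to either declared hypothesis.
- *The inflation is at least about 24%.* Rare infections or strong correlation take it well below that, and an exact test lowers it further.

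What the reply does not remove is the text itself: the comparisons sit under the primary-outcome sentence, and no available sentence makes them descriptive. The background also reports the earlier pediatric lansoprazole work infection by infection, with separate odds ratios for upper respiratory infection and sore throat each marked p < 0.05. A claim about one infection would follow that pattern.

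**Conclusion.** The point holds as an unresolved endpoint hierarchy with a multiplicity consequence. The Overview, the assessment section and the Statistical analysis paragraph disagree on what the primary safety outcome is, and the item-level comparisons have neither a rank nor an error control.

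If they are tested as the text suggests, a trial of 30 children per arm with no dosing effect yields at least one nominally significant infection about 13-34% of the time. The upper end fits common infections with weak correlation, and the lower end fits mostly rare ones. The result rests on the inferred 0.05 level, 1:1 allocation, the uncorrected chi-squared test, and assumed risks and correlations. The existence of the gap does not depend on those assumptions; only its size does.

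**What to change.** 1. Reconcile the composite to one definition, including its components and the population in which it is tested. The Overview and the Statistical analysis paragraph currently differ: only the latter restricts it to poor metabolizers, and the infection components are worded differently.
2. In the assessment section, replace the sentence on comparing each symptom with text such as: *The reconciled adverse-effect composite is the only confirmatory safety comparison. The eight individual infections are exploratory and are reported by arm as counts and risk differences with 95% confidence intervals, without claims of significance.*
3. If claims on single infections are wanted, prespecify Holm's procedure across the eight. The smallest p-value would then be compared with 0.05/8 = 0.00625.

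An additional endpoint of any of the eight infections should not be introduced. It would differ from both existing composites, which include kidney effects and fractures, and would add to the conflict.

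The cost is a few sentences and no new data. The downside is that a single infection can no longer be claimed as a finding from its own unadjusted p-value.
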